2.1 List of Tables

Table 3-1	Abbreviations and Definitions of Terms	6
[REDACTED]	[REDACTED]	
[REDACTED]	[REDACTED]	

[REDACTED]	[REDACTED]
Table 5-1	Analysis Populations..... 15
Table 5-2	Statistical Methodology 15
Table 5-3	Missing Data Handling by Endpoint Type..... 16
Table 5-4	Analysis Population Summaries 17
Table 5-5	Subject Disposition Summaries 17
Table 5-6	Protocol Deviation Summary..... 18
Table 5-7	Demographic Summaries..... 18
Table 5-8	Baseline Characteristics Summaries 19
Table 5-9	Medical History 19
Table 5-10	Medication 19
Table 5-11	Exposure to Study Treatment..... 20
Table 5-12	Administration of Study Treatment 20
Table 5-13	Effectiveness Assessments..... 21
Table 5-14	Effectiveness Endpoint Baseline Definitions..... 21
Table 5-15	Primary Effectiveness Analyses..... 21
Table 5-16	Secondary Effectiveness Analyses..... 21
[REDACTED]	[REDACTED]
Table 5-18	AE Terms 21
Table 5-19	AE Summaries 21

[REDACTED]	[REDACTED]
Table 5-26	Sample Size Assumptions
Table 6-1	Analysis Day Definitions.....

[REDACTED]	[REDACTED]
[REDACTED]	[REDACTED]

3. List of Abbreviations and Definition of Terms

Table 3-1 Abbreviations and Definitions of Terms

Abbreviation/Term	Definition
3D	3-dimensional
ACRS	Allergan Chin Retrusion Scale
ADE	Adverse Device Effect
AE	Adverse Event
CFR	Code of Federal Regulations
CI	Confidence Interval
eCRF	Electronic Case Report Form
EI	Evaluating Investigator
DFU	Directions For Use
FDA	Food and Drug Administration
GAIS	Global Aesthetic Improvement Scale
HA	Hyaluronic Acid
HIPAA	Health Insurance Portability and Accountability Act
IC	Informed Consent
ICF	Informed Consent Form
ICH	International Conference on Harmonisation
IRB	Institutional Review Board
ISO	International Organization for Standardization
ISR	Injection Site Response
ITT	Intent-to-treat
IWRS	Interactive Web Response System
mITT	modified Intent-To-Treat
PP	Per-Protocol
PT	Preferred Term
SADE	Serious Adverse Device Effect
SOC	System Organ Class
TI	Treating Investigator
UADE	Unanticipated Adverse Device Effect
US	United States

4. Introduction

This statistical analysis plan (SAP) details comprehensive, technical specifications of the statistical analyses of the effectiveness and safety data outlined and/or specified in the protocol of Study VOLUMA-006 (Amendment 4 version dated 2017-03-01). This SAP will be approved prior to database lock.

4.1 Study Design Summary

10

1000

Country	Percentage of the population aged 65+ in 2010
Austria	21.5%
Belgium	21.5%
Bulgaria	21.5%
Cyprus	21.5%
France	21.5%
Germany	21.5%
Greece	21.5%
Hungary	21.5%
Italy	21.5%
Malta	21.5%
Portugal	21.5%
Spain	21.5%
Sweden	21.5%
Switzerland	21.5%
United Kingdom	21.5%

Term	Percentage
GDP	100
Inflation	98
Interest rates	95
Central bank	92
Monetary policy	90
Quantitative easing	88
Inflation targeting	85
Interest rate hike	82

4.1.2 Number of Participants

Up to 224 subjects will be enrolled at up to 15 sites.

[figure not shown]
4.2 Study Objectives and Endpoints

The objectives of this study are to evaluate the safety and effectiveness of JUVÉDERM VOLUMA XC injectable gel in augmentation of chin retrusion in adult subjects seeking improvement in chin volume deficit.

Each study primary objective, secondary objective, and other objectives are presented with corresponding endpoint(s) below:

Table 4-1 Study Objectives and Corresponding Endpoints

Objectives	Endpoints

• To evaluate and compare the effectiveness of JUVÉDERM VOLUMA XC injectable gel with no treatment control in augmentation of chin retrusion in adult subjects seeking improvement in chin volume deficit• To evaluate the safety of JUVÉDERM VOLUMA XC injectable gel in augmentation of chin retrusion in adult subjects seeking improvement in chin volume deficit	
Primary Endpoint :
 
• Responder rate based on photo assessment of the Allergan Chin Retrusion Scale (ACRS) at month 6 
Secondary Endpoints:
 
• Change from baseline in overall scores of the Satisfaction with Chin module of the FACE-Q questionnaire at month 6• Responder rate based on Evaluating Investigator (EI) assessment of global aesthetic improvement scale (GAIS) in the chin area at month 6• Responder rate based on subject assessments of the GAIS in the chin area at month 6 

5. Statistical Methodology and Study Endpoints

5.1 Statistical and Analytical Plans

Statistical analyses will be conducted using [REDACTED]

5.1.1 Common Conventions

5.1.1.1 Analysis Populations

The analysis populations will consist of subjects as defined below:

Table 5-1 Analysis Populations

Population	Definition	Study Treatment
Intent-to-Treat (ITT)	All randomized subjects	Randomized assignment
Modified Intent-to-Treat (mITT)	
• All subjects randomized to the treatment (treatment group) who receive at least 1 study treatment• All subjects randomized to the control group	Randomized assignment
Per-Protocol (PP) population	All mITT subjects who do not have any significant protocol deviations affecting the primary effectiveness endpoint	Randomized assignment
Safety	
• All subjects randomized to the treatment (treatment group) who receive at least 1 study device treatment• All subjects randomized to the control group	Actual received

Unless specified otherwise, all effectiveness analyses will be performed on the mITT population using the “as-randomized” assignment for each subject (ie, if a subject randomized to the control group is treated inadvertently at the start of the study, the assessments for that subject will nonetheless be included in the control group analysis). The ITT and PP populations will be used to perform sensitivity analyses for the primary effectiveness variable. All safety analyses will be conducted using the safety population.

5.1.1.2 Study Treatments

The following treatment groups are defined for this study:

- Study Treatment: JUVÉDERM VOLUMA XC injectable gel
- Control Treatment: Delayed treatment

5.1.1.3 Statistical Methodology

The methodologies defined below apply as specified to individual endpoints defined in this SAP.

Table 5-2 Statistical Methodology

Methodology	Description
Categorical counts	
 Number and percent of subjects in individual categories 
 Subjects with ≥ 1 qualifying event counted once per individual category N included = participants with non-missing value for by visit analysis
Event descriptives	
 Number and percentage of events in individual categories 
 Events counted individually for each instance Percentage denominator = total number of events
Continuous descriptives	
 N included, mean, standard deviation (SD), median, minimum, maximum N included = subjects with non-missing value
CFB descriptives	
 Continuous descriptives for baseline, postbaseline, and change from baseline (CFB) values N included = subjects with non-missing values at both baseline and the specified postbaseline analysis visit
CFB Paired T	
 Continuous descriptives for baseline, postbaseline, and CFB values 
 P-values from a 2-sided paired t-test comparing baseline and postbaseline values N included = subjects with non-missing values at both baseline and the specified postbaseline analysis visit
Responder	
 Categorical descriptives for responders and nonresponders 
 Include count and percent along with exact binomial 95% CI P-values from 2-sided Fisher's exact test N included = with non-missing values at both baseline and the specified postbaseline analysis visit

5.1.1.4 Missing Data

General missing data handling conventions are specified and summarized as follows:

Table 5-3 Missing Data Handling by Endpoint Type

Endpoint type	Timing	Missing Data Handling
Responder	Month 6 (no-treatment control period)	
 All subjects included (ITT population) Multiple imputation with 5 imputed datasets is applied to subjects with no postbaseline values using the below model: $\text{Month 6 ACRS} = \beta_0 + \beta_1 \text{Baseline ACRS} + \beta_2 \text{Month 1 ACRS} + \beta_3 \text{Month 3 ACRS}$ 
where ACRS score is based on photo assessment.

Responder	Month 6 (no-treatment control period)	
 All subject included (ITT population) Last observation carried forward (LOCF) for subjects with no postbaseline values

The above missing data handling conventions will only be used for sensitivity analysis of the primary effectiveness endpoint.

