Every attempt will be made to collect complete data and limit the occurrence of missing data. No imputation of missing data will be performed. Deviations from the analyses planned in the statistical plan will be documented in the clinical study report.

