8.1 Analysis Populations

The following analysis populations will be used in the analyses for this study:

- intent-to-treat (ITT) population: all randomized subjects
- modified intent-to-treat (mITT) population: subjects who are randomized to study treatment (treatment group) and receive at least 1 study device treatment or are randomized to the control group
- per-protocol (PP) population: all mITT subjects who do not have any significant protocol deviations affecting the primary effectiveness endpoint
- safety population: all subjects randomized to treatment (treatment group) who receive at least 1 study device treatment and all subjects randomized to control group

Unless specified otherwise, all effectiveness analyses will be performed on the mITT population using the “as-randomized” assignment for each subject (ie, if a subject randomized to the control group is treated inadvertently at the start of the study, the assessments for that subject will nonetheless be included in the control group analysis). The ITT and PP populations as well as missing data imputation will be used to perform sensitivity

analyses for the primary effectiveness variable. Additionally, sensitivity analysis will be performed on mITT subjects with a baseline ACRS photo score of 2 or 3. All safety analyses will be conducted using the safety population.

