8.5 Sample Size Calculation

A sample size of 120 subjects in the treatment group and 40 subjects in the control group will provide > 99% power to detect a difference of at least 40% in the responder rates between the groups. This calculation is based on a 2-sided Fisher's exact test at the 5% level. The treatment group is assumed to have at least 80% responder rate and the control group will have at most 40% responder rate. Assuming a screen fail rate of 15% and a drop-out rate of 15% between randomization and the month 6 visit, up to 224 subjects will be enrolled, resulting in up to 168 subjects randomized to the treatment group and up to 56 subjects to the control group (3:1 ratio). Assuming a screen fail rate of 15% and an overall drop-out rate of 20% between randomization and study completion, an estimated 152 subjects will complete the study.

With up to 168 subjects randomized to the treatment group and an estimated screen fail rate of 15%, it is estimated that at least 143 subjects will be treated in the study. With 143 treated subjects, there is at least an 88% power to detect an AE related to treatment with an incidence rate of 1.5% in the population using a 1-sided exact binomial test at the 2.5% level.

Due to an estimated 15% of subjects having a baseline photo assessment of 1 or 4, up to 36 additional subjects may be randomized to ensure sufficient power for sensitivity analyses, resulting in a total of up to 260 subjects enrolled.

The commercial software, PASS (2008, Version 8.0.13), was used for the power calculation. The sample size calculation used an inequality test for 2 proportions to demonstrate that the treatment group is superior to the control group. The safety calculation used an inequality test for 1 proportion.

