5.1.3.1 Primary Effectiveness Endpoint

The primary effectiveness endpoint will be met if the responder rate at month 6 for the treatment group is statistically greater than that for the control group at month 6 and the observed responder rate at month 6 for the treatment group is greater than 50%. A responder is a subject who shows clinically significant improvement, i.e., ≥ 1 -point decrease, on the ACRS from baseline based on EI assessment of 2D renderings of the chin profile.

The primary effectiveness analysis is summarized in Table 5-15.

Table 5-15 Primary Effectiveness Analyses

Endpoint	Description	Timing	Methodology
Primary: Responder analysis based on photo ACRS	
• Superiority of the treatment group over no-treatment control group• Responder rate of treatment group is greater than 50%	Month 6	Responder

The primary effectiveness analysis will be performed on the mITT population without any missing data imputation. Sensitivity analysis will be performed using ITT and PP populations as well as using missing data handling conventions as described in Section 5.1.1.1.4. Additionally, sensitivity analysis will be performed on mITT subjects with a baseline ACRS photo score of 2 or 3.

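### Both missing-data rules in SAP Table 5-3 skip drop-outs who have an interim score but no Month 6 score, and the imputation model has no treatment-arm term

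*SAP*

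**What the plan says.** SAP 5.1.3.1 runs the primary responder analysis on the mITT population with no imputation, then adds: "Sensitivity analysis will be performed using ITT and PP populations as well as using missing data handling conventions". Those conventions are in SAP 5.1.1.4, Table 5-3, which has two rows. Both concern the Month 6 responder endpoint, and both state that every ITT subject is included.

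- Row 1: "Multiple imputation with 5 imputed datasets is applied to subjects with no postbaseline values using the below model". The model is linear in baseline, Month 1 and Month 3 photo ACRS. It contains no treatment term, and imputation by arm is not mentioned.
- Row 2: "Last observation carried forward (LOCF) for subjects with no postbaseline values".

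The responder method in SAP Table 5-2 sets the denominator: "N included = with non-missing values at both baseline and the specified postbaseline analysis visit".

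The protocol says two things about imputation. The opening text of Section 8 says: "No imputation of missing data will be performed". Section 8.1 says: "The ITT and PP populations as well as missing data imputation will be used to perform sensitivity" analyses of the primary variable. Protocol 8.5 plans for "a drop-out rate of 15% between randomization and the month 6 visit".

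**The concern.** There are four difficulties, in order of weight.

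1. **Coverage.** A subject with a Month 1 or Month 3 score does have a post-baseline value. If that subject lacks Month 6, neither rule applies, and Table 5-2 removes the subject from the denominator. The promise of full ITT inclusion then fails.
2. **Self-contradiction.** Everyone whom row 1 covers lacks Month 1 and Month 3 by definition, so two of its three predictors are missing for every target subject. For the same people, LOCF can carry forward only the baseline score, which makes each of them a non-responder.
3. **No arm term.** A subject with only a baseline score is imputed at roughly the pooled responder rate in either arm, which pulls the two arms together.
4. **Protocol conflict.** One sentence rules out all imputation, while another requires it for sensitivity analyses.

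These are the only planned imputation checks on a complete-case primary analysis. If most drop-outs have an interim visit, both checks nearly reproduce the complete-case result and could be reported as robustness that was never tested.

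**Working it through.** **Inputs.** Protocol 8.5: responder rates 80% and 40%; 120 and 40 evaluable; screen failure 15%; drop-out f = 15% by Month 6; 2-sided Fisher's exact test at 5%. Protocol 4.5: 3:1 allocation. The documents do not give s, the share of drop-outs with no post-baseline score, so it is varied from 0 to 100%.

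**The plan's own figures reproduce.** Exact Fisher power at 120 versus 40 is 99.5%, matching the stated > 99%. Enrolment is 160/(0.85 × 0.85) = 221.5, or 166.1 and 55.4 by arm, which 168 + 56 = 224 covers at 3:1.

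**Subjects affected.** 224 × 0.85 = 190.4 randomised, and 190.4 × 0.15 = 28.6 lack Month 6. If 25%, 50%, 75% or 100% of these have an interim score, about 7, 14, 21 or 28 are imputed by neither rule.

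**Literal reading.** Pooled rate: 0.75 × 80% + 0.25 × 40% = 70%. For an arm with true rate p:

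- MI without arm: [(1 − f)p + f·s·0.70] / [(1 − f) + f·s]
- LOCF as written (all imputed are non-responders): (1 − f)p / [(1 − f) + f·s]

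| s | Left out (% of randomised) | MI without arm | LOCF as written | Difference, either rule (points) |
|---|---|---|---|---|
| 0% | 15% | 80.0% vs 40.0% | 80.0% vs 40.0% | 40.0 |
| 25% | 11.25% | 79.6% vs 41.3% | 76.6% vs 38.3% | 38.3 |
| 50% | 7.5% | 79.2% vs 42.4% | 73.5% vs 36.8% | 36.8 |
| 75% | 3.75% | 78.8% vs 43.5% | 70.6% vs 35.3% | 35.3 |
| 100% | 0% | 78.5% vs 44.5% | 68.0% vs 34.0% | 34.0 |

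Worked line, s = 100%: treatment 0.85 × 0.80 + 0.15 × 0.70 = 0.785; control 0.85 × 0.40 + 0.15 × 0.70 = 0.445. Fisher power stays at 98.2% or more in every cell. LOCF as written does stress the treated rate, but it lowers the control rate as well. At s = 100% with f of 5% or 10%, the difference is 38 or 36 points.

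**Reading the rule as no Month 6 value.** This was simulated with 400,000 subjects per run. The assumptions, none of them in the documents except the 15% figures, were: 15% of baselines at 1 or 4, 15% missing at random, a pooled linear fit plus residual noise, and scores rounded to 0–4. With Month 1 and Month 3 observed and no arm term:

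| Assumed within-subject correlation | Imputed responder rate, treatment / control | Overall difference (points) |
|---|---|---|
| 0.3 | 74.1% / 53.7% | 37.4 |
| 0.5 | 75.1% / 49.9% | 38.1 |
| 0.7 | 76.3% / 46.8% | 38.3 |
| 0.85 | 77.4% / 44.2% | 39.1 |

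With arm in the model the difference is 39.5 to 40.2. The loss is therefore about 1 to 3 points.

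**A borderline illustration of the coverage gap.** Take 143 versus 48 randomised, with 21 and 7 lacking Month 6. Complete cases: 71/122 (58.2%) versus 16/41 (39.0%), Fisher p = 0.046. Suppose all 28 drop-outs have an interim score showing no improvement. Ordinary LOCF gives 71/143 (49.7%) versus 16/48 (33.3%), p = 0.065, which would miss both success criteria. Table 5-3 as written imputes none of the 28 and returns p = 0.046 again.

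**The case against.** The strongest reply is that the SAP uses post-baseline to mean the value at the row's own visit. The change-from-baseline rows of Table 5-2 and the Month 6 FACE-Q row of Table 5-16 use it that way, and both rows of Table 5-3 are timed at Month 6. The Month 1 and Month 3 predictors, the name LOCF and the claim of full ITT inclusion all fit a rule meant for subjects with no Month 6 value. That is plausible and probably the intent. It would close the coverage gap and set aside the literal-reading table and the borderline example. However, the SAP does not say it, the plural wording points the other way, and it leaves the missing arm term and the handling of missing interim scores unresolved.

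The illustration is also a knife edge. Its 58.2% is far from the planned 80%, and it assumes that none of the 28 improved. One more treated responder gives 72/122 versus 16/41 (p = 0.031) and, under LOCF, 72/143 (50.3%) versus 16/48 (p = 0.046), so both criteria pass. It shows what the rule can fail to detect, not what is likely.

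Materiality is limited too. These rules serve sensitivity analyses only, and reversal is unlikely at the planned rates. The SAP already works out the protocol's conflict in practice, with no imputation in the primary analysis and imputation in the sensitivity analyses. All of that stands. It limits the severity but does not make Table 5-3 workable as written.

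**Conclusion.** The concern holds and should be fixed. As written, Table 5-3 leaves partial drop-outs out of both analyses, specifies predictors that its targets cannot have, and omits treatment arm. At 80% versus 40% with 15% drop-out, the result lies between an exact copy of the complete-case analysis (40 points) and a 34-point difference, depending on a share that the documents do not give. On the more generous reading, the missing arm term alone costs about 1 to 3 points, conditional on the assumed correlations and score distribution. The bias towards zero from omitting arm assumes that missingness is unrelated to outcome. The coverage gap is not conservative, because it can make a check agree with the primary result simply by leaving out the subjects in question. The success criteria are unaffected.

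**What to change.** Before database lock:

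- Define the target of both rules in SAP Table 5-3 as every ITT subject without a Month 6 photo ACRS.
- Run the multiple imputation separately by randomised arm, or put arm in the model, and impute missing Month 1 and Month 3 scores first.
- Define LOCF as the last available post-baseline score, with non-response where there is none.
- Limit the sentence in the opening text of protocol Section 8 to the primary analysis, so that it agrees with protocol 8.1 and SAP 5.1.3.1.

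The cost is SAP wording, one protocol sentence and a few lines of code. No new data or subjects are needed.

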5.2 Determination of Sample Size

The sample size assumptions and estimate are summarized as follows:

Table 5-4 **Sample Size Assumptions**

Parameter	Assumption / Estimate
Primary endpoint	Chin retraction assessment responder
Risk difference ¹	40 (80% Voluma vs 40% Control)
SD	NA
α	5%
Sides	2
Power	>99%
N per group	120 in Voluma group, 40 in control group
Screen Fail Rate	15%
Drop-out Rate	15%
N total	224

¹ Based on literature/previous study VOLUMA-002 and relevant details.

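### The multiple-imputation model in SAP Table 5-3 has no treatment term, so as printed it imputes early withdrawals in both arms alike and shrinks the difference in this sensitivity analysis

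*SAP*

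**What the plan says.** SAP 5.1.1.4, Table 5-3, gives two rules for a missing Month 6 response in the ITT population.

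- **Multiple imputation.** "Multiple imputation with 5 imputed datasets is applied to subjects with no postbaseline values using the below model". The model is linear in three predictors: the baseline, Month 1 and Month 3 ACRS photo scores. Treatment is not among them, and the section does not say whether the fit is across arms or within arm.
- **LOCF.** "Last observation carried forward (LOCF) for subjects with no postbaseline values".

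Their role is limited: "The above missing data handling conventions will only be used for sensitivity analysis of the primary effectiveness endpoint". SAP 5.1.3.1 agrees: "The primary effectiveness analysis will be performed on the mITT population without any missing data imputation". It then lists sensitivity analyses on the ITT and PP populations, "as well as using missing data handling conventions as described in" the missing-data section, and on subjects with a baseline photo score of 2 or 3.

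The planning rates are in protocol 8.5: "The treatment group is assumed to have at least 80% responder rate and the control group will have at most 40% responder rate". Allocation is 3:1 (protocol 4.5).

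**The concern.** An imputation model should contain the variables in the analysis it feeds. Here the analysis compares arms, and the model omits the arm. The Month 1 and Month 3 scores could stand in for it when they are observed, because treated chins will have changed by then. The rule, however, is written for subjects who have neither score. For them baseline is the only observed predictor, and it carries no information about the arm after randomisation.

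A withdrawn control is then imputed mostly from treated subjects' outcomes, and a withdrawn treated subject partly from controls' outcomes. The analysis is there to show whether missing data could alter the primary answer. If the model itself moves the estimate when withdrawals are harmless, a reader cannot tell a model artefact from an effect of missing data.

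The section that follows, SAP 5.1.1.5, does name treatment assignment as a predictor in the site model, so its absence from Table 5-3 cannot be read as implied.

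**Working it through.** **Inputs**

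- Responder rates: 80% treatment, 40% control (protocol 8.5; SAP 5.2).
- Allocation 3:1 (protocol 4.5).
- Evaluable subjects: 120 and 40. Two-sided Fisher's exact test at 5% (protocol 8.5).
- Screen failure 15% and drop-out to month 6 15% (protocol 8.5).
- Subjects left after screen failure: 168 × 0.85 = 142.8, the plan's 143, for treatment; 56 × 0.85 = 47.6, taken as 48, for control.
- Share *d* with no postbaseline photo: **not in the documents**. Assumed 5% to 15%, equal in both arms. The upper end would need every drop-out before month 6 to leave before any follow-up photo.

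**The plan's own figures**

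Exact enumeration of the Fisher test at 120 and 40 gives 99.5% power, in line with the stated > 99%. Evaluable numbers are 168 × 0.85 × 0.85 = 121.4 and 56 × 0.85 × 0.85 = 40.5, which match 120 and 40.

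**Imputed response without an arm term**

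With baseline scores balanced by randomisation, the fitted population is three parts treated to one part control:

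q = (3 × 0.80 + 1 × 0.40) / 4 = 0.70 in both arms.

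The response should be 0.80 for treated subjects and 0.40 for controls.

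**Effect on the difference**

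Treatment: 0.80(1 − d) + 0.70d. Control: 0.40(1 − d) + 0.70d. Difference: 0.40(1 − d).

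| d | Treatment | Control | Difference | Fisher power at 143 and 48, imputed values treated as observed |
|---|---|---|---|---|
| 5% | 79.5% | 41.5% | 38.0 points | 99.8% |
| 10% | 79.0% | 43.0% | 36.0 points | 99.5% |
| 15% | 78.5% | 44.5% | 34.0 points | 98.9% |

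The value q cancels from the difference. Any rule that gives the missing subjects of both arms the same response rate yields 0.40(1 − d). LOCF is such a rule here: carrying baseline forward makes each of these subjects a nonresponder. At d = 15% it gives 0.80 × 0.85 = 68% against 0.40 × 0.85 = 34%, again 34 points. Agreement between the two rules would therefore not corroborate either.

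**Simulation check**

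Setup: 143 and 48 subjects, 600 trials, five imputations, withdrawal at random, an assumed mix of baseline scores, Months 1, 3 and 6 imputed in sequence by normal regression, and imputed scores rounded to a grade.

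| Model | Difference, d = 5% | Difference, d = 15% | Imputed response at d = 15%, treatment / control |
|---|---|---|---|
| No arm term | 37.6 | 34.0 | 70.2% / 70.0% |
| Arm term added | 39.9 | 39.6 | 79.7% / 43.5% |
| Fitted by arm | 39.7 | 39.8 | 78.5% / 41.4% |

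An arm term or a by-arm fit removes almost all of the loss. The small remainder depends on the assumed baseline mix and the rounding.

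**Never-injected subjects**

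ITT includes treatment-arm subjects who were never injected; mITT does not. If their true response were the control rate (an assumption), the printed model would overstate it by 70 − 40 = 30 points per such subject. A model with an arm term would overstate it by about 80 − 40 = 40 points. The documents give no expected number of these subjects.

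**The case against.** The best defence has four parts.

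1. **It is only a sensitivity analysis.** No success criterion uses it, and the same endpoint is also examined by LOCF, ITT, PP and the baseline 2-or-3 subset. This stands, and it limits the severity.
2. **The error is conservative.** For withdrawals at random the shift is toward no difference, at most 6 points, with power still 98.9% and a treatment rate far above 50%. This also stands, except for never-injected subjects.
3. **The SAP does not say the fit is across arms.** True. A by-arm fit would remove the problem, but a programmer following the printed model has no instruction to do that.
4. **The covered group may be loosely worded.** Month 1 and Month 3 predictors serve little purpose for subjects who lack both, so the rule may be meant for anyone missing Month 6. If those two scores are observed, they carry much of the arm information. Simulation at 15% missing, with assumed within-subject correlation of 0.3 to 0.85, gives about 37 to 39 points without an arm term and about 38 to 40 with one, so the term is worth at most about 3 points. This is a fair reading, but not what Table 5-3 says. On that reading the wording of who is covered has to change. On the literal reading the SAP must say how Months 1 and 3 are obtained.

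A reader might infer that the trial's efficacy conclusion is biased, or biased in the device's favour. The documents do not support that: the primary analysis uses no imputation, and ordinary withdrawals pull the estimate toward zero. A reader might also take 34 points as the expected result. It is the extreme of an assumed range, because the 15% in protocol 8.5 counts all drop-out to month 6.

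**Conclusion.** Wrong as written, and it should be fixed. It does not threaten the trial. Followed literally, the Table 5-3 imputation gives withdrawals in both arms the same response distribution given baseline and reduces a true 40-point difference to 40(1 − d): 38, 36 or 34 points at 5%, 10% or 15% with no postbaseline photo.

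These figures rest on the planning rates, 3:1 allocation, a fit across arms, equal withdrawal in both arms, and data missing completely at random. The bias disappears if the arms do not differ or if the fit is by arm. What is lost is the purpose of the check, because part of any gap from the primary result would come from the model.

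**What to change.** In SAP Table 5-3:

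1. Add randomised treatment to the imputation model, or state that imputation is done separately by arm.
2. Apply the rule to all subjects missing the Month 6 photo score, including those with some earlier follow-up photos, whom neither rule now covers.
3. State that missing Month 1 and Month 3 scores are imputed in sequence within the same procedure, before Month 6.
4. State how treatment-arm subjects who were never injected are handled in this ITT analysis, since an arm term alone would impute them as if treated. Imputing them from the control arm is one option. It is a choice of estimand on which statisticians may differ, so it needs a stated reason.

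The cost is one model term (or a by-arm statement), a few sentences and a small programming change. No new data are needed and the primary analysis does not change. SAP section 4 places approval before database lock, which is when this should be settled.
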